4.2.6 Healthcare Resource Utilization Assessment related to HAE (HRUA-HAE)

The usage of healthcare resources related to HAE in the last month (HRUA-HAE) is assessed (every four weeks) with a 5-item questionnaire collecting:

- i. Number of hospital admissions
- ii. Number of healthcare provider visits
- iii. Number of tests required
- iv. Number of emergency medicine unit or out-of-hours care clinic visits
- v. Number of days of home care

The total number of hospital admissions, healthcare provider visits, tests required, emergency/out-of-hours clinic visits, and days of home care will be calculated, using the information collected in the HRUA-HAE, for the duration of each study period by summing all of the responses to each individual item during each period.

4.3 Study Assessments

The administration of study measures for each study period will follow the schedule of assessments provided in the study protocol (see Table 1 and Table 2). The PRO measures will be completed using the electronic subject diary and will be assessed as follows:

AE-QoL: Administered every 4 weeks on weeks 1 (prior to treatment administration), 5, 9, and 13, of each study period. It will also be administered at the early discontinuation visit, if applicable, and at the 1-week post-treatment visit.

EQ-5D-5L: Administered on weeks 1 (prior to treatment administration), and 12, of each study period, and on each day subjects experience signs or symptoms of AE attack. It will also be administered at the early discontinuation visit, if applicable, and at the 1-week post-treatment visit.

WPAI-GH: Administered on week 1 (prior to treatment administration) and once a week, for the duration of each study period. It will also be administered at the early discontinuation visit, if applicable, and at the 1-week post-treatment visit.

SDS: Administered on week 1 (prior to treatment administration) and once a week, for the duration of each study period. It will also be administered at the early discontinuation visit, if applicable, and at the 1-week post-treatment visit.

AAS: Administered daily. It will also be administered at the early discontinuation visit, if applicable, and at the 1-week post-treatment visit.

HRUA-HAE: Administered on weeks 1 (prior to treatment administration), 4, 8, and 12, of each study period. It will also be administered at the 1-month post-treatment visit.

Shire HRQoL Statistical Analysis Plan Protocol SHP616-300

22 Aug 2017

Table 1: Schedule of Assessments – Study period 1

													STUD	OY PE	RIOD) 1 (B)	Y STU	DY W	EEK))									
			1		2		3		4		5		6		7		8	ç)	1	.0	1	1		12	1	3	14	4
														DOS	ING V	/ISIT:	S (1a to	o 28a)											
Procedures	Screen ^a	1a	2a	3a	4 a	5a	6a	7a	8 a	9a	10a	11a	12a	13a	14a	15a	16a	17a	18a	19a	20a	21a	22a	23a	24a	25a	26a	27a	28a
Informed consent	~																												
Medical history	~																												
Inclusion/Exclusion criteria	~	✔ c																											
Adverse events ^b	~		¥																									~	
Randomization (predose)		✓ c																											
Physical examination	~	✓ c							~								<								•				~
Prior/concomitant meds	~	✓ c	~	~	~	~	~	~	~	~	~	~	~	<	~	~	<	~	~	~	~	<	~	<	<	~	<	~	~
Height and body weight	~																												
Vital signs (BP, pulse) ^{d, e}	~	~	~	~	~				~								~								~				~
12-lead ECG ^d	~																												
Safety labs ^f	~	✓ c							~								<								>				~
UA with microscopy		✓ c																											~
Virology screening ^g	~																												
Pregnancy testing ^h	~	✓ c																											
IP injection		✓ ⁱ	>	>	>	~	>	>	✓ ⁱ	~	>	>	>	>	>	>	✓ ⁱ	~	>	<	>	>	>	>	✓ ⁱ	>	<	>	✓ ⁱ
ISR assessment ^j		~	>	~	>	~	>	~	√ j	~	<	~	~	>	>	~	✓j	~	>	<	<	>	<	>	✔ j	<	<	~	✔ j
Acceptability surveyk																													~
Self-administration survey ^k																													~
Angioedema attack			¥																									····· `	~
monitoring ^{k, 1}																													
AAS ^k			×																									·· `	/
AE-QoL questionnaire ^k		✓ c								~								~								~			
EQ-5D-5L ^{k, m,}		✓ c																							~				
WPAI-GH and SDS ^k		✓ c		~		~		~		~		~		~		~		~		~		~		~		~		~	
HRUA-HAE		✓ c							~								~								~				
Anti-C1 INH antibodies		✓ c							✓ c								✓ c								✓ c			✔ c,n	∨ c,n
PK/PD sampling														Se	e prot	tocol													

22 Aug 2017

Table 1: Schedule of Assessments – Study period 1

																												_
												STUD	Y PERI	OD	1 (BY	STU	DY W	EEK)										1
		1		2		3		4		5		6	7		8	3	9)	10		11	1	2	1	3	1	4	٦
													DOSIN	G VI	ISITS	(1a to	28a)											٦
Procedures	Screen ^a	1a	2a	3a	4a	5a (Sa (7a 8	Ba S	9a 10a	a 1	1a 12a	13a 14	4a	15a	16a	17a	18a	19a 20	a 21	a 22a	23a	24a	25a	26a	27a	28a	1
AAS=angioedema activity	score; AE	-QoL:	L=angioedema quality of life; aPPT=activated partial thromboplastin time; BP=blood pressure; C1 INH=C1 esterase inhibitor; CRF=case report form;																									
ECG=electrocardiogram; E	EQ-5D-5L	L=EuroQol 5-dimensional 5-level descriptive system; HAE=hereditary angioedema; HIV=human immunodeficiency virus; HRUA=health resource																										
utilization assessment; INF	R=internat	ional r	norma	alized	ratio	; IP=in	vestig	ationa	l pro	duct; IS	R=i	injection	site read	ctior	n; PD	=phar	maco	dynai	nic; PK=	-phar	macoki	netic;	PT=pi	rothro	mbin 1	ime;		
SDS=Sheehan Disability S	cale; UA=	-urinal	lysis;	WPA	I-GH	I=Worl	rod	uctivi	ty and	d Activ	ity I	Impairme	ent Gene	eral	Healt	h Que	estion	naire		-			-					
^a All subjects will have a se	creening e	valuat	tion v	vithin 2	21 da	avs pric	r to th	ne firs	t dose	e of invo	estig	gational	product	(Vis	sit 1a=	=Dosi	ng Da	av 1).										

All subjects will have a screening evaluation within 21 days prior to the first dose of investigational product (Visit Ta–Dosing Day I

^b Adverse events will be collected from the time of informed consent through 7 days after the last dose of investigational product.

^c Specified procedures should be performed prior to investigational product administration.

^d Vital signs and ECGs will be measured using standard methods at each study site. Additional vital signs measurements and ECGs may be performed during the study if clinically indicated.

^e On dosing days, vital signs should be measured \leq 30 min before the start of the injection, \leq 10 min after the end of the injection, and then between 30 min and 1 h after the end of the injection.

^f Biochemistry, hematology, and coagulation (aPPT, PT, INR, D-dimer). In addition, D-dimer should be evaluated in any subject who presents at a study visit with signs and symptoms consistent with suspected venous thromboembolism.

^g HIV (single assay antibody/INNO-LIA) and hepatitis (Hepatitis B Surface Antigen, Hepatitis C Antibody).

^h Female subjects of childbearing potential; serum pregnancy test at screening and urine pregnancy test at all other time points.

ⁱ Investigational product will be administered by qualified personnel at the investigational site at Dosing Visits 1a, 8a, 16a, 24a, and 28a.

^j Injection site reaction assessments will be performed 15 min, 30 min, and 1 h after the end of the injection. At Visits 8a, 16a, 24a, and 28a an overall assessment of injection site severity (mild, moderate, and severe as defined in Section 11.1 in main study SAP) and the overall duration of the injection site reactions will be captured in the CRF.^k In the electronic subject diary.

¹ The investigator will complete a separate angioedema attack CRF for each attack based upon their review of the data in the subject diary.

^m In addition to the scheduled time points, subjects should complete the EQ-5D-5L on each day that they experience signs or symptoms of an angioedema attack.

ⁿ Collection of blood sample for the immunogenicity assessment should coincide with the subject's PK/PD sampling schedule and will occur at either Visit 27a or Visit 28a (see Table 5 in main study SAP).

Table 2:Schedule of Assessments – Study period 2

											ST	UDY	PERIC	DD 2 (E	SY STU	JDY W	/EEK)										
		1		2	3	1	4		5		6		7		8		9		10		11		12		13		14	
Procedures					_						_	DC	DSING	VISIT	'S (1b 1	to 28b)												
	1b	2b	3b	4b	5b	6b	7b	8b	9b	10b	11b	12b	13b	14b	15b	16b	17b	18b	19b	20b	21b	22b	23b	24b	25b	26b	27b	28b
Adverse events ^a		✓																									· ¥	
Physical examination	✓ b							~								~								~				~
Concomitant medications	~	~	~	~	~	~	~	~	~	~	~	~	~	~	~	~	~	~	~	~	~	~	~	~	~	>	~	~
Body weight	~																											
Vital signs (BP, pulse) ^c	~	~	~	~				~								~								~			ļ!	~
Safety labs ^d	✓ b							~								~								~				~
UA with microscopy	✔ b																											~
Pregnancy testing ^e	✓ b																											
IP injection	√ f	>	>	<	~	•	>	√ f	~	<	~	>	~	~	>	∨ f	•	>	~	>	>	>	~	√ f	>	>	~	∨ f
ISR assessment ^g	•	>	>	<	~	•	>	✓ g	~	<	~	>	~	~	>	✓ g	•	>	~	>	>	>	~	✔ g	>	>	~	✓ g
Acceptability survey																												~
Self-administration survey ^h																												~
Angioedema attack		✓																									· ¥	
monitoring ^{h, 1}																												
AAS ⁿ		×																									~	
AE-QoL questionnaire ^h	✓ Ь								~								~								~			
EQ-5D-5L ^{h, j}	✓ b																							~				
WPAI-GH and SDS ^h	✓ b		~		~		~		~		~		~		~		~		~		~		~		~		~	
HRUA-HAE	✓ b							~								~								~				
Anti-C1 INH antibodies	✓ b							∨ ^b								∨ ^b								✔ ^b				✓ b
PK/PD sampling														See p	rotocol													

AAS=angioedema activity score; AE-QoL=angioedema quality of life; aPPT=activated partial thromboplastin time; BP=blood pressure; C1 INH=C1 esterase inhibitor; CRF=case report form; ECG=electrocardiogram; EQ-5D-5L=EuroQol 5-dimensional 5-level descriptive system; HAE=hereditary angioedema; HRUA=health resource utilization assessment; INR=international normalized ratio; IP=investigational product; ISR=injection site reaction; PD=pharmacodynamic; PK=pharmacokinetic; PT=prothrombin time; SDS=Sheehan Disability Scale; UA=urinalysis; WPAI-GH=Work Productivity and Activity Impairment-General Health Questionnaire

Note: ECGs may be performed during Study period 2 if clinically indicated, using standard methods at each study site.

^a Adverse events will be collected from the time of informed consent through 7 days after the last dose of investigational product.

^b Specified procedures should be performed prior to investigational product administration.

^c Vital signs will be measured using standard methods at each study site. Additional vital signs measurements may be performed during the study if clinically indicated. On dosing days, vital signs should be measured \leq 30 min before the start of the injection, \leq 10 min after the end of the injection, and then between 30 min and 1 h after the end of the injection.

^d Biochemistry, hematology, and coagulation (aPPT, PT, INR, D-dimer). In addition, D-dimer should be evaluated in any subject who presents at a study visit with signs and symptoms consistent with suspected venous thromboembolism.

^e Urine pregnancy test for female subjects of childbearing potential.

^f Investigational product will be administered by qualified personnel at the investigational site at Dosing Visits 1b, 8b, 16b, 24b, and 28b.

22 Aug 2017

Table 2:Schedule of Assessments – Study period 2

		STUDY PERIOD 2 (BY STUDY WEEK)																										
	1	1	2	2	3		4		5		6		7		8		9		10		11		12		13		14	
Procedures												DO	SING V	ISITS	S (1b to	28b)												
	1b	2b	3b	4b	5b	6b	7b	8b	9b	10b	11b	12b	13b 1	4b	15b	16b	17b	18b	19b	20b	21b	22b	23b	24b	25b	26b	27b	28b
^g Injection site reaction asse	ssmen	ıt will	be per	rform	ed 15 1	min, 3	30 min,	and 1	h afte	er the	end of	the ir	jection.	At V	Visits 8	b, 16ł	o, 24b,	and 2	28b an	overa	all asso	essme	nt of i	njecti	on site	severi	ity (m	ld.

moderate, and severe as defined in Section 11.1 in the main study SAP) and the overall duration of the injection site reactions will be captured in the CRF. ^h In the electronic subject diary.

ⁱ The investigator will complete a separate angioedema attack CRF for each attack based upon their review of the data in the subject diary.

^j In addition to the scheduled time points, subjects should complete the EQ-5D-5L on each day that they experience signs or symptoms of an angioedema attack.

5. DATA MANAGEMENT

5.1 Data Handling Considerations

5.1.1 Data Analysis Populations

The analyses will use data from the full analysis data set: all enrolled subjects randomized to treatment sequence AB or BA who completed at least the baseline data collection. Subjects enrolled in the AA sequence will be included in the analyses where stated.

5.1.2 Baseline data

For analyses using mixed models, a common baseline will be taken as visit 1a. For other analyses, as appropriate, the baseline visit will be the baseline for each specific study period: visit 1a will be the baseline visit for period 1, and visit 1b will be the baseline visit for period 2.

5.1.3 Missing Data

Frequencies will be used to evaluate missing data and measures will be scored in accordance with the instrument developers' recommendations listed below:

- AE-QoL: Domains can be calculated if no more than 1 item is missing and the total score if no more than 25% of items (> 4 items) are missing (Weller et al., 2012).
- EQ-5D-5L: Index scores cannot be calculated if any of the five dimensions is missing (Simons et al., 2015).
- EQ-VAS: EQ-VAS score cannot be calculated if the EQ-VAS is not completed at an assessment.
- WPAI GH: Scores cannot be calculated if there is a missing response to a corresponding item (Reilly Associates, 2002).
- SDS: No established conventions exist but since the Global functioning impairment score is comprised of only three items, the score will not be calculated if at least one of the three dimensions is missing.
- AAS: Total scores can be calculated so long as no more than a week (7 days) of data are missing (Weller et al., 2013).

Imputation of missing data will be limited to end of treatment data used in the calculation of change scores. In the event that a subject is missing end of treatment data, the closest available score to the period end or discontinuation will be used so long as the value was obtained a minimum of 9 weeks past the period start date. If not available, no change score will be calculated. No other missing data will be imputed.

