6.2 Administration of Investigational Product

Blinded investigational product (C1 esterase inhibitor [human] liquid for injection or placebo) will be administered twice weekly (every 3 or 4 days) for 14 weeks in each of 2 separate treatment periods. Every effort should be made to complete scheduled dosing and to avoid situations where investigational product is not received. In order to prevent a missed dose, a less than 3-day interval may occur, with the recommendation of allowing at least 24 hours between doses. The contents of 2 vials of investigational products (a total volume of 4 mL) will be drawn into a silicone-free syringe for each SC injection. Following appropriate SC injection site selection and preparation ([Appendix 2](#)), the needle will be inserted in the subject's abdominal area in order to administer the SC injection as quickly as tolerated by the subject.

Investigational product will be administered at the investigational site for Dosing Visits 1, 8, 16, 24, and 28 during both treatment periods. Other doses may be administered by qualified blinded personnel at the investigational site or at the subject's home or other agreed upon location or self-administered by the subject (adolescent or adult) with or without supervision (qualified home health professional and/or study site personnel), after receiving appropriate training by the investigator or designee. Adolescent subjects self-administering investigational product will be supervised by a parent/legal guardian/caregiver (if a qualified home health professional and/or study site personnel is not present). Alternatively, a parent/legal guardian/caregiver after

receiving appropriate training will be allowed to administer the investigational product to an adolescent subject with or without supervision.

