7.1.2.3 Visit 2a through Visit 28a

The following procedures will be performed throughout Treatment Period 1 at the visits indicated below:

- All concomitant medication and AEs will be recorded at each visit (2a-28a)
- Recording in the electronic subject diary daily any symptoms or occurrences of an angioedema attack (Visits 2a-28a)
- Recording the daily AAS in the electronic subject diary (Visits 2a-28a)
- Vital signs ≤ 30 min predose; ≤ 10 min and between 30 min and 1 hour after the injection (Visits 2a, 3a, 4a, 8a, 16a, 24a, 28a). Note: Vital sign measurements are not required at Visits 2a, 3a, and 4a for subjects self-administering investigational product without supervision (ie, assessment may not be possible).
- Physical examination (Visits 8a, 16a, 24a, 28a)
- Investigational product will be administered at each visit (2a-28a); Visits 8a, 16a, 24a, and 28a must occur at the investigational site.
- Injection site reaction assessment will be performed 15 min, 30 min, and 1 hour after investigational product administration at Visits 8a, 16a, 24a, and 28a. At Visit 28a, the overall impact of injection site reactions on daily living (yes/no) and duration will be assessed.
- Clinical laboratory testing (biochemistry, hematology, coagulation) at Visits 8a, 16a, 24a, and 28a
- Urinalysis testing with microscopy at Visit 28a

- Acceptability and self-administration survey assessment (recorded in the electronic subject diary) at Visit 28a
- Quality of life assessments recorded in the electronic subject diary: AE-QoL (Visits 9a, 17a, 25a), EQ-5D-5L (Visit 24a and on each day that a subject experiences signs or symptoms of an angioedema attack), and WPAI-GH and SDS (Visits 3a, 5a, 7a, 9a, 11a, 13a, 15a, 17a, 19a, 21a, 23a, 25a, 27a)
- HRUA-HAE (Visits 8a, 16a, 24a)
- Immunogenicity (anti-C1 INH antibody) (predose Visits 8a, 16a, 24a, 27a or 28a)
- PK/PD sampling (C1 INH antigen, C1 INH functional, and C4) (predose Visits 2a, 8a, 16a, 24a, 27a or 28a [within \approx 15 min], and 48 h postdose Visits 27a or 28a [\pm 3 hours]). Note: A predose Visit 2a blood sample is not required for subjects self-administering investigational product without supervision (ie, sample collection may not be possible).

7.1.3 Treatment Period 2

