- Kaplan-Meier estimate of time to initial improvement and time to complete resolution since onset of attack by attack order during the treatment period.

The treatment differences in clinical responder rates, both of which are defined within treatments, i.e., the difference in the proportions of subjects with a clinical response to C1 INH

or placebo, each of them will be analyzed using McNemar's test for testing equality of proportions of responders within treatments.

Cumulative attack severity, cumulative daily severity, number of attack-free days during a treatment period and the 98-day AAS will be analyzed using a linear mixed effect model with period, sequence, use of prophylactic therapy with C1 INH, which is derived by long-term prevention with C1 INH at randomization, and treatment as fixed effects, and subject nested within sequence as a random effect. If the variance-covariance matrix of random effects is not positive definite, a mixed effect model with the same fixed effects and subject nested within sequence as repeated measurements will be performed instead. The results will be summarized by the point estimate of within-subject treatment differences or response rates and the corresponding 95% CI.

Kaplan-Meier analysis will be performed on all subjects in the Full Analysis Set without censoring. Median, 25%, 75% quartiles and their CI's will be estimated for time to initial improvement / complete resoluction since acute treatment administration / onset of attack.

Summary statistics (n, mean, SD, median, minimum and maximum) will be provided on each dimension and total score of AE-QoL by treatment and visit. A table will be provided summarizing the change from baseline to each visit and the last observation recorded within the treatment period for a subject's response to each dimension and the total score of AE-QoL.

In addition, angioedema attacks will be summarized by the maximum symptom severity of the attack and treatment for all subjects in the Full Analysis Set. Acute angioedema attacks will be summarized by acute therapy, the maximum symptom severity of the attack and treatment for all subjects in the Full Analysis Set.

Cumulative attack severity, cumulative daily severity and number of attack-free days will be plotted by treatment for the subjects who are randomized to the first two treatment sequences (A/B or B/A) in the Full Analysis Set.

Details on derivation of normalized efficacy variables are provided in the Appendix.

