10.2 Calculating Change in Scores

Change in scores will be calculated as follows for each visit and each study period separately:

- Study period 1:
 - Follow up visit x score baseline (visit 1a) score
- Study period 2:
 - Follow up visit x score baseline (visit 1b) score

Change in AAS scores will be calculated as follows:

- Study period 1:
 - Weekly average daily scores for the each week of follow up baseline (visit 1a) daily score
- Study period 2:
 - Weekly average daily scores for the each week of follow up baseline (visit 1b) daily score

The overall change score is always the final follow up visit minus the baseline visit, for each study period separately. For AAS scores, it is change from baseline to the weekly average daily score in the final week, for each study period separately.

Imputation of missing data will be limited to end of treatment data used in the calculation of change scores. In the event that a subject is missing end of treatment data, the closest available score to the period end or discontinuation will be used so long as the value was obtained a minimum of 9 weeks past the period start date. If not available, no change score will be calculated. No other missing data will be imputed.

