10.3 Responder Definition Variables

A RD binary variable will be created for each relevant PRO measure (AE-QoL, and EQ-5D-5L) and score. Each person will receive a 0 if they did NOT reach the MCID or estimated distribution-based RD for the PRO measure and score in the relevant study period, and they will receive a 1 if they did.

- AE-QoL
 - \circ Rescaled AE-QoL total score = 6, Baseline SD*0.5
 - \circ Rescaled AE-QoL Functioning domain score = 6, Baseline SD*0.5
 - \circ Rescaled AE-QoL Fatigue/mood domain score = 6, Baseline SD*0.5

- Rescaled AE-QoL Fear/shame domain score = 6, Baseline SD*0.5
- Rescaled AE-QoL Nutrition domain score = 6, Baseline SD*0.5
- EQ-5D-5L
 - EQ-5D-5L Index Score = 0.05, 0.075, 0.10, 0.125, Baseline SD*0.5
 - \circ EQ-VAS Score = 5, 7.5, 10, Baseline SD*0.5
- AAS
 - Average daily scores = 1, Baseline SD*0.5.

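### The HRQoL SAP's 9-week minimum for a substitute end-of-treatment score shuts out the Week 9 AE-QoL, which is due 8 weeks after period start

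*SAP*

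**What the plan says.** HRQoL SAP 5.1.3 limits imputation to end-of-treatment values used in change scores. The score nearest to period end or discontinuation may stand in, and is "used so long as the value was obtained a minimum of 9 weeks past the period start date". Otherwise: "If not available, no change score will be calculated". HRQoL SAP 10.2 repeats the rule for programming.

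The AE-QoL schedule is in HRQoL SAP 4.3: "AE-QoL: Administered every 4 weeks on weeks 1 (prior to treatment administration), 5, 9, and 13, of each study period". Protocol 7.1.2.3 places the post-baseline assessments at Visits 9a, 17a and 25a, Protocol 7.1.3.3 does the same for Period 2, and HRQoL SAP 6.4.1 labels Visit 17 as week 9 and Visit 25 as week 13. Under Protocol 6.2, product is "administered twice weekly (every 3 or 4 days) for 14 weeks in each of 2 separate treatment periods". AE-QoL is also taken at the early discontinuation visit and the 1-week post-treatment visit (Protocol Table 3), and before dosing at Visit 1b (Protocol 7.1.3.1).

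The change score is the outcome of the AE-QoL mixed models in HRQoL SAP 6.4.1, and the responder variable in HRQoL SAP 10.3 is built on it: "Each person will receive a 0 if they did NOT reach the MCID" or the distribution-based threshold. Main SAP 10.4 summarises AE-QoL change to each visit and to "the last observation recorded within the treatment period for a subject's response to each dimension and the total score of AE-QoL", with no minimum time.

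**The concern.** The label Week 9 means the first visit of the ninth study week, when only eight weeks have elapsed. A rule written in elapsed weeks with the number nine therefore excludes the one scheduled on-treatment AE-QoL that could replace Week 13. The wording suggests that the label and the elapsed time were confused, though the text does not say so.

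What is at stake is who enters the AE-QoL models, and with which value. AE-QoL is a secondary efficacy endpoint (Protocol 9.8.2.2). Main SAP 10.4 gives it descriptive summaries and leaves it off its list of mixed-model endpoints, so HRQoL SAP 6.4.1 holds its only modelled analysis. Subjects may also stop for reasons linked to the outcome: Protocol 4.4.1 lists lack of efficacy, and Protocol 5.2.1 allows certain subjects to be discontinued after at least 3 weeks if attacks and quality of life worsen.

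**Working it through.** **Elapsed time.** With two doses a week the mean interval is 3.5 days, so visit *k* falls (*k* - 1) x 3.5 days after period start. The study-week label is the number of whole weeks elapsed plus 1.

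| AE-QoL visit | Days after period start | Weeks elapsed | Label | At least 63 days? |
|---|---|---|---|---|
| 9 | 8 x 3.5 = 28 | 4.0 | Week 5 | no |
| 17 | 16 x 3.5 = 56 | 8.0 | Week 9 | no, 7 days short |
| 25 | 24 x 3.5 = 84 | 12.0 | Week 13 | yes (the value being replaced) |

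The formula reproduces the labels in HRQoL SAP 6.4.1. The threshold is 9 x 7 = 63 days.

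**Range.** If all 16 intervals were 3 days, Visit 17 would fall at 48 days; if all were 4 days, at 64. It reaches 63 only if the mean interval is at least 63/16 = 3.94 days, or if doses are delayed. A Week 9 score would then qualify because the subject ran late.

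**Other measures.** WPAI-GH and SDS are taken at Visit 19, at 18 x 3.5 = 63 days, which just qualifies. AAS is daily. The mismatch is specific to AE-QoL.

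**Other AE-QoL scores that could meet the rule.**
- Early discontinuation score at 63 to 83 days: accepted. At 56 to 62 days: refused. Of the 84 days before Week 13, the rule accepts such scores on 84 - 63 = 21; a cut-off at the Week 9 visit would accept them on 84 - 56 = 28.
- Week 13 missed but treatment continued, Period 1: Visit 1b predose, at 28 x 3.5 = 98 days. The wording does not exclude it, although it is also the Period 2 baseline in HRQoL SAP 10.2.
- Week 13 missed but treatment continued, Period 2: the 1-week post-treatment visit, at 27 x 3.5 + 7 = 101.5 days.

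**Worked case.** A subject's last dose is 59 days after period start and the discontinuation visit is that day. The Week 9 score (56 days, 8.0 weeks) and the discontinuation score (59 days, 8.4 weeks) are both refused. The 1-week post-treatment score, due at 59 + 7 = 66 days (plus or minus 1), passes the 63-day test. If that visit is missed, there is no change score for the period. Main SAP 10.4 would use the last observation within the treatment period.

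**Responder variable.** HRQoL SAP 10.3 speaks of each person receiving 0 or 1; HRQoL SAP 5.1.3 leaves some periods without a change score. Whether such a period is coded 0 or missing is not stated, and the denominator depends on it.

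**The case against.** The strongest reply is that few subjects need be lost. Continuing subjects who miss Week 13 have Visit 1b or the 1-week post-treatment score. Those who stop from 63 days with a discontinuation score are kept. Anyone whose last dose is at 56 days or later is due a post-treatment AE-QoL at about 63 days or later, and its 4-week recall (Protocol 7.2.4.2) covers mostly treated time. Requiring a minimum exposure before calling a score end-of-treatment is a legitimate choice, and main SAP 12.3 defers quality-of-life details to a separate plan, so a descriptive last-value row there need not match.

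Most of this stands. A reader might infer that everyone who stops or misses Week 13 drops out, so that the AE-QoL models become close to a completers' comparison with treatment failures removed. The documents do not support that: the routes above keep many such subjects, no figure is given for the rest, and no direction of bias is shown. Subjects who stop before 56 days lack a qualifying score whether the cut-off is 56 or 63 days.

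What remains is that the plan never says whether Visit 1b or post-treatment scores count, attendance after discontinuation is asked for only where possible, and the literal rule can set aside two on-treatment scores for one taken off treatment. A minimum exposure is defensible; one that misses the scheduled visit of the same number by 7 days needs to be shown to be intended.

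**Conclusion.** The mismatch holds: the Week 9 AE-QoL is nominally 7 days too early for the rule. The affected subjects are those who stop between about 56 and 63 days after period start, and those with a Week 9 score but no later AE-QoL. Each loses one period's change and responder score, or has it rest on an off-treatment value. The other period and the visit-level summaries are untouched.

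The number cannot be computed. The planning figures give only an upper bound on planned non-completion: 26 + 26 = 52 randomised to the crossover sequences and 44 completing (main SAP 2.1 and 2.5) leave 8, or 15%, stopping at any time in either period. How many fall in this window is not given, and missed visits among subjects who continue are not counted in it.

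This assumes nominal dosing and a literal reading of 9 weeks. The point is minor for the trial: AE-QoL is outside the tested hierarchy, and success rests on the primary endpoint alone (main SAP 10.3).

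**What to change.** In HRQoL SAP 5.1.3 and 10.2:

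1. For AE-QoL only, replace the 9-week minimum with: *at or after the Week 9 visit (Visit 17, nominally 56 days after period start), including early discontinuation scores from that day*. The other measures can keep the present rule.
2. State whether Visit 1b predose and 1-week post-treatment scores may serve as end-of-treatment values.
3. In HRQoL SAP 10.3, state how the responder variable treats a period that was started but has no qualifying score. Coding it 0 or missing are both possible; the choice should be fixed before unblinding.
4. Add a sensitivity run of the AE-QoL change models using the last observation within the treatment period, as in main SAP 10.4.

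The cost is a few sentences and one extra run. The downside is that some end-of-treatment values will come from 8 weeks rather than 12.
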